## 9. PHARMACOKINETIC ANALYSES

Due to poor absorption of volixibat very low systemic exposure and plasma drug levels are expected. Volixibat plasma concentrations will be summarized using descriptive statistics by analysis visit and dose of volixibat received at the specified analysis visit.

For maternal volixibat plasma concentration assessments: Plasma concentration of volixibat near predicted maximum observed concentration ( $C_{max}$ ) will be obtained during the Week 1 visit, approximately 3 hours after dosing. Trough plasma levels of volixibat will be obtained during the Week 3 visit before dosing. Contingent upon meaningful exposures of volixibat, PK endpoints may include but are not limited to  $C_{max}$ , time to reach  $C_{max}$  ( $T_{max}$ ), and the area under the plasma concentration-time curve (AUC) from time zero to the last measurable time point. Actual dosing and sampling times will be used for calculation of PK parameters. Additional PK parameters may be calculated.

For fetal (umbilical cord) volixibat plasma concentration assessments: Plasma concentration of volixibat in the umbilical cord blood sample obtained at delivery will be collected (when possible) and analyzed.

Plasma volixibat concentrations will also be presented in participants listings.

## **11. SOFTWARE**

SAS® Software Version 9.4. SAS Institute Inc., Cary, NC, USA.

R Software Version 4.0.3 (or later). The R Foundation. Vienna, Austria.

## 12. SAP REVISION

Revision Date (DD MMM YYYY)	Section	Summary of Revision	Reason for Revision

### 13. APPENDIX 1 SCHEDULE OF ACTIVITIES

**Table 7 Schedule of Activities**

Visit Name	Screening	Treatment Period				Follow-Up		Notes
		Baseline	Week 1, 2, 3, etc.	Early Term*	EOT/Delivery	F1	F2 (EOS)	
Day/Week (Window)	Day -10 to -1	0*	Every 7 Days (±1 Day) Until Delivery		Day of Delivery (+2 Days)	Phone Call: 14 Days after Delivery (±2 Days)	Clinic Visit: 28 Days after Delivery (±3 Days)	*Participants who early terminate from study drug should still continue with weekly visits through delivery, F1, and F2.  Some visits may be conducted as a home health or remote visit at the discretion of the investigator upon approval by the medical monitor or designee and in accordance with local and regional regulations.  *Regardless of date of screening visit, baseline visit must occur no later than 35 weeks and 0 days gestational age.
Administrative Procedures								
Informed consent	X							
Eligibility Procedures								
Inclusion/exclusion criteria	X	X						
Demography	X							
Prior/concomitant treatment	X	X	X	X	X	X	X	
Medical history	X	X						Includes menstrual and obstetric history
Estimated gestational age assessment	X							Confirmation of eligibility based upon estimated gestational age required before randomization: CRL from early ultrasound or head circumference on ultrasound if CRL is >84 mm.
Hepatitis and HIV screen, TSH	X							
Dosing Procedures								
Randomization		X						
Study treatment dispensing		X	X					As needed
Study treatment collection/reconciliation			X	X	X			As needed

Visit Name	Screening	Treatment Period				Follow-Up		Notes
		Baseline	Week 1, 2, 3, etc.	Early Term*	EOT/Delivery	F1	F2 (EOS)	
Day/Week (Window)	Day -10 to -1	0*	Every 7 Days (±1 Day) Until Delivery		Day of Delivery (+2 Days)	Phone Call: 14 Days after Delivery (±2 Days)	Clinic Visit: 28 Days after Delivery (±3 Days)	
*Participants who early terminate from study drug should still continue with weekly visits through delivery, F1, and F2.
 
Some visits may be conducted as a home health or remote visit at the discretion of the investigator upon approval by the medical monitor or designee and in accordance with local and regional regulations.
 
*Regardless of date of screening visit, baseline visit must occur no later than 35 weeks and 0 days gestational age.

Efficacy Procedures								
Education and compliance assessment of pruritus assessments	X	X	X					Education regarding importance of eDiary compliance at screening visit; reinforcement regarding eDiary compliance at study visits (as needed).
Once daily Adult ItchRO score assessment	X	X	X	X	X			Participant completes ItchRO at home on eDiary up to and including the day of delivery.
Pruritus/QoL PRO assessments (5D itch scale, CSS, EQ-5D-5L, PROMIS SF v1.0-Fatigue 7a, PROMIS SF v1.0-Sleep Disturbance, PIS-Itch)		X	X*	X	X**			
Participant completes at clinic, except CSS, which the investigator completes at clinic.
 
All PRO assessments to be completed by participant, including PIS-Itch and PGIC-Itch, should be collected prior to additional procedures at study visits.
 
*At Week 3 visit only
 
**For participants who terminate from study drug early, this does not need to be repeated.

PGIC-Itch			X*	X	X**			
Participant completes at clinic.
 
*At Week 3 visit only
 
**For participants who terminate from study drug early, this does not need to be repeated.

Other Procedures								
Health utilization		X		X			X	
Safety Procedures								
Drug and alcohol screen	X							
Hematology panel	X		X	X	X		X	
Chemistry	X		X	X	X		X	

Visit Name	Screening	Treatment Period				Follow-Up		Notes
		Baseline	Week 1, 2, 3, etc.	Early Term*	EOT/Delivery	F1	F2 (EOS)	
Day/Week (Window)	Day -10 to -1	0*	Every 7 Days (±1 Day) Until Delivery		Day of Delivery (+2 Days)	Phone Call: 14 Days after Delivery (±2 Days)	Clinic Visit: 28 Days after Delivery (±3 Days)	*Participants who early terminate from study drug should still continue with weekly visits through delivery, F1, and F2.  Some visits may be conducted as a home health or remote visit at the discretion of the investigator upon approval by the medical monitor or designee and in accordance with local and regional regulations.  *Regardless of date of screening visit, baseline visit must occur no later than 35 weeks and 0 days gestational age.
Physical examination	X	X	X	X	X		X	Complete examination conducted at screening and F2 visits. A symptom-directed examination focused on changes from last examination conducted at other visits. Includes confirmation of fetal cardiac activity via Doppler/auscultation at each visit while participant is pregnant.
Height	X							
Weight	X	X	X	X	X		X	
ECG	X							
Vital signs	X	X	X	X	X		X	
Coagulation (PT/INR, PTT)	X		X	X	X		X	
Vitamin A, D, and E levels		X	X*		X		X	*Every 4 weeks, starting with Week 4 visit. The sample collection tube should be protected from light.
Urinalysis	X	X	X	X	X		X	
Lipid panel, glycated albumin	X		X*		X		X	*Every 2 weeks, starting with Week 2 visit
sBA	X	X*	X*	X	X**		X	At each visit except EOT/Delivery, must be drawn in the non-fasting state (e.g., postprandially), 30-90 minutes after start of a meal. Every effort should be made to collect postprandial sBA levels at approximately the same time of day (morning, midday, or afternoon) at each visit starting with baseline, except for EOT/delivery.  *At baseline and Week 3, an additional fasting sBA must be performed.  **At EOT/Delivery, sBA may be performed without regard to last meal.
AE review		X	X	X	X	X	X	AEs for mother and baby to be collected and reviewed for up to 30 days after respective dates of hospital discharge.

Visit Name	Screening	Treatment Period				Follow-Up		Notes
		Baseline	Week 1, 2, 3, etc.	Early Term*	EOT/Delivery	F1	F2 (EOS)	
Day/Week (Window)	Day -10 to -1	0*	Every 7 Days (±1 Day) Until Delivery		Day of Delivery (+2 Days)	Phone Call: 14 Days after Delivery (±2 Days)	Clinic Visit: 28 Days after Delivery (±3 Days)	
*Participants who early terminate from study drug should still continue with weekly visits through delivery, F1, and F2.
 
Some visits may be conducted as a home health or remote visit at the discretion of the investigator upon approval by the medical monitor or designee and in accordance with local and regional regulations.
 
*Regardless of date of screening visit, baseline visit must occur no later than 35 weeks and 0 days gestational age.

Fetal ultrasound	X*	X*	X*					*Every 4 weeks while on study treatment; first ultrasound may be done during screening OR baseline (both are not required)
Antepartum fetal monitoring (NST/CTG or BPP)		X*	X*					*At baseline and Week 1 visits only, and thereafter at the discretion of the investigator
Perinatal outcomes assessment					X			
Outcomes include
 
 
• Gestational age at delivery
 
• Mode of delivery (e.g., vaginal, operative vaginal, Cesarean, etc.; and iatrogenic vs. spontaneous)
 
• Indication(s) for delivery, if iatrogenic
 
• Apgar score at 5 minutes
 
• Infant/placenta weight
 
• Maternal estimated blood loss at delivery
 
• Presence/absence of meconium staining of amniotic fluid
 
• Neonatal diagnoses and data, including NICU data if applicable
 

Umbilical cord sample (at delivery, when possible)					X			Umbilical artery pH should be assessed first, followed by volixibat pharmacokinetics. Thereafter, sBA, total cholesterol, LDL cholesterol, and glucose can be assessed in any order.
Genetics - maternal blood (optional)		X						Specific testing TBD. Must confirm specific consent has been obtained for genetic testing
Genetics – cord blood sample (optional)					X			Specific testing TBD. Must confirm specific consent has been obtained for genetic testing.
NICU admission					X	X	X	Collect NICU admissions diagnoses and data for the duration of NICU stay (i.e., follow to resolution).

Visit Name	Screening	Treatment Period				Follow-Up		Notes
		Baseline	Week 1, 2, 3, etc.	Early Term*	EOT/Delivery	F1	F2 (EOS)	
Day/Week (Window)	Day -10 to -1	0*	Every 7 Days (±1 Day) Until Delivery		Day of Delivery (+2 Days)	Phone Call: 14 Days after Delivery (±2 Days)	Clinic Visit: 28 Days after Delivery (±3 Days)	*Participants who early terminate from study drug should still continue with weekly visits through delivery, F1, and F2.  Some visits may be conducted as a home health or remote visit at the discretion of the investigator upon approval by the medical monitor or designee and in accordance with local and regional regulations.  *Regardless of date of screening visit, baseline visit must occur no later than 35 weeks and 0 days gestational age.
Drug Levels/Biomarkers Procedures								
Volixibat concentration sample (maternal plasma)			X*	X	X			*At Week 1 visit, 3 hours (+/- 15 minutes) post-dose; at Week 3 visit, ≤60 minutes pre-dose When feasible, maternal sample should be collected as close to time of actual delivery as possible. Drug level sampling may be discontinued in Part 2 pending Part 1 results
Volixibat concentration sample (fetal plasma from umbilical cord at delivery, when possible)					X			Drug level sampling may be discontinued in Part 2 pending Part 1 results
Biomarker samples (maternal) • C4 (fasting and postprandial, 30-90 min) • FGF-19 (fasting) • Autotaxin (fasting) • Progesterone sulfate • GLP-1 (fasting)		X*	X*		X**			*Baseline and at Week 3 visit only **Random C4 only, timed with sBA draw at EOT/Delivery visit

5-D Itch; Adult Itch RO; AE=adverse event; BPP=biophysical profile; C4=7 $\alpha$ -hydroxy-cholesten-3-one; CRL=crown rump length; CSS=Clinician Scratch Scale; CTG=cardiotocography; eDiary=electronic diary; EOS=end of study; EOT=end of treatment; EQ-5D-5L=EuroQoL 5-Dimension 5-Level; ET=early termination; F1=follow-up Visit 1; F2=follow-up Visit 2; ItchRO=Itch Reported Outcome; NICU=neonatal intensive care unit; NST=nonstress test; PGIC-Itch=Patient Global Impression of Change-Itch; PIS-Itch=Patient Impression of Severity of Itch; PRO=patient-reported outcome; PROMIS=Patient-Reported Outcomes Measurement Information System; PT=prothrombin time; PTT=partial thromboplastin time; QoL=quality of life; sBA=serum bile acids; SF=short form; TBD=to be determined; TSH=thyroid-stimulating hormone.

## 14. APPENDIX 2 ADVERSE EVENTS OF SPECIAL INTEREST AND CLINICAL INTEREST

The following event is an AESI for participants in this study:

- Symptomatic cholelithiasis
- Threatened preterm labor

The following events are ECIs in this study:

- Diarrhea (CTCAE Grade  $\geq 3$ )
  - MedDRA preferred terms include the following:
    - Diarrhoea
- Abdominal pain (CTCAE Grade  $\geq 3$ )
  - MedDRA preferred terms include the following:
    - Abdominal pain
    - Abdominal pain lower
    - Abdominal pain upper
- Transaminase increases (CTCAE Grade  $\geq 3$ )
  - MedDRA preferred terms include the following:
    - Alanine aminotransferase abnormal
    - Alanine aminotransferase increased
    - Aspartate aminotransferase abnormal
    - Aspartate aminotransferase increased
    - Bilirubin conjugated abnormal
    - Bilirubin conjugated increased
    - Blood bilirubin abnormal
    - Blood bilirubin increased
    - Blood bilirubin unconjugated increased

- Liver function test abnormal
- Liver function test increased
- Transaminases abnormal
- Transaminases increased
- Fat-soluble vitamin deficiency
  - MedDRA preferred terms include the following:
    - Vitamin A decreased
    - Vitamin A abnormal
    - Vitamin A deficiency
    - Vitamin D decreased
    - Vitamin D abnormal
    - Vitamin D deficiency
    - Vitamin E decreased
    - Vitamin E abnormal
    - Vitamin E deficiency
    - Vitamin K decreased
    - Vitamin K abnormal
    - Vitamin K deficiency
    - International normalised ratio increased
    - International normalised ratio abnormal

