#### **9.2.7. Events of Clinical Interest**

ECIs will include CTCAE Grade  $\geq 3$  diarrhea, CTCAE Grade  $\geq 3$  abdominal pain, CTCAE Grade  $\geq 3$  transaminase increases, and fat-soluble vitamin deficiency; these will be subject to specialized, targeted data collections. Please refer to [Appendix 3](#) for algorithms to assess transaminase increases and/or potential DILI events.

Additional ECIs may be identified during the course of the study.

Specifics regarding events to be designated as ECIs, along with reporting instructions/timelines, will be included in the eCRF completion guidelines. ECIs that meet seriousness criteria shall be subject to expedited reporting as outlined in [Sections 9.2.1](#) and [9.2.5](#).

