##### **10.4.2.1. Adverse Events**

In general, TEAEs are defined as AEs that start or deteriorate on or after the first dose of study medication and no later than 7 days following the last dose of study medication. For any participants (i.e., expectant mothers) who die during the study and the date of death is between the date of the first dose of study medication and the date of study discontinuation (as entered by the site), inclusive, all AEs (including those resulting in death) that occur during the study will be considered as TEAEs irrespective of the last dose and will be included in the TEAE summaries. All summaries of AEs will be based on TEAEs unless specified otherwise.

The complete list of Preferred Terms for AESIs and ECIs (as described in [Sections 9.2.6](#) and [9.2.7](#)) will be outlined in the SAP and summarized.

AEs will be coded using MedDRA. The number and proportion of participants who experience the event according to MedDRA System Organ Class (SOC) and Preferred Term will be presented by treatment group.

The incidence of all AEs and treatment-related AEs will be tabulated by treatment received. These AEs will be classified by SOC and Preferred Term using MedDRA. AEs will be graded using the CTCAE, Version 5.0, grading scale. For incidence reporting, if a participant reported >1 AE that was coded to the same SOC or Preferred Term, the participant will be counted only once for that specific SOC or Preferred Term. An overview of AEs and TEAEs, both of which include participant incidence of AEs, treatment-related AEs, AEs by severity, AESIs, ECIs, SAEs, deaths, and AEs that lead to discontinuation, will be presented.

Furthermore, exposure-adjusted incidence rates (EAIR) will be provided for each AE reported. For EAIR analyses, the following convention will be used to calculate the denominator (i.e., population-level time at-risk) for these analyses. The population-level time at-risk includes only the time each participant is at risk. The start date of at-risk time is the date of first dose of study drug, and the last date of at-risk time is the start date of the occurrence of the AE or is censored at completion/early termination, whichever is earlier.

While no formal hypothesis testing or margin selection is planned, the risk difference and corresponding exact 95% CI (using the method of Chan and Zhang [1999]) will be presented to compare treatment groups with regards to AESIs and ECIs.

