### **7.1.7. Additional Analysis of Adverse Events**

Furthermore, exposure adjusted incidence rates (EAIR) will be provided for each AE reported. For EAIR analyses, the following convention will be used to calculate the denominator (i.e., population-level time at-risk) for these analyses. The population-level time at-risk includes only the time each participant is at risk. The start date of at-risk time is the date of first dose of study drug, and the last date of at-risk time is the start date of the occurrence of the AE or is censored at completion/early termination, whichever is earlier.

While no formal hypothesis testing or margin selection is planned, the risk difference and corresponding exact 95% CI (using the method of Chan and Zhang [1999]) will be presented to compare treatment groups with regards to AESIs and ECIs.

The TEAE by PT summary will also be repeated by the subgroups defined in [Section 3.4](#).

Incidence/prevalence plots of common adverse events may be explored.

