## **7.6. Changes From Protocol-Specified Safety Analyses**

There are no deviations from the protocol-specified safety analyses.

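### SAP Appendix 2 defines the ECI 'transaminase increases' with 13 terms, 7 of which are not transaminase terms, so the category is wider than the protocol's ECI

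*SAP*

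**What the plan says.** Protocol Section 9.2.7 lists four ECIs. The liver item is CTCAE Grade ≥3 transaminase increases, at the end of a list that reads "transaminase increases, and fat-soluble vitamin deficiency; these will be subject to specialized, targeted data collections". Bilirubin is not named. The section refers to Appendix 3 for transaminase increases and possible drug-induced liver injury, allows further ECIs to be identified, and leaves reporting specifics to the eCRF completion guidelines. Protocol Section 10.4.2.1 says that the complete preferred-term list for the ECIs described in Section 9.2.7 "will be outlined in the SAP and summarized".

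SAP Appendix 2 supplies that list. Under its Grade ≥3 transaminase heading it also includes "Bilirubin conjugated increased", "Blood bilirubin unconjugated increased" and "Liver function test abnormal".

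SAP Section 7.1.6.1 summarises ECIs as the number and percentage of participants, counting each participant once per summary, by system organ class and preferred term, with a brief overview table. SAP Section 7.1.7 plans a risk difference with an exact 95% CI that "will be presented to compare treatment groups with regards to AESIs and ECIs", prefaced by "While no formal hypothesis testing or margin selection is planned". SAP Section 7.6 states: "There are no deviations from the protocol-specified safety analyses".

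**The concern.** The label and its contents describe different events. A reader of an ECI row headed transaminase increases will take it as the proportion of participants with a Grade ≥3 rise in ALT, AST or transaminases, because that is what the protocol promises. On the SAP's list, the row can include participants whose transaminases never reached Grade 3.

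Protocol Appendix 3 keeps these measures apart. ALT is the index measure, bilirubin is a concurrent parameter, and different actions follow from ALT alone, bilirubin alone and both together. Treating the terms as interchangeable loses that distinction.

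What is at stake is the meaning of one planned safety comparison. The primary endpoint, the testing hierarchy and alpha are not affected.

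**Working it through.** **Term count (SAP Appendix 2).**

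| Group | Terms | Count |
|---|---|---|
| ALT, AST, transaminases | each as abnormal and increased | 6 |
| Bilirubin | conjugated abnormal and increased; blood bilirubin abnormal and increased; unconjugated increased | 5 |
| General liver function test | abnormal and increased | 2 |
| Total | | 13 |

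Outside the protocol's wording: 5 + 2 = 7 of 13.

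**Plan's own figures.** Neither document gives an ECI rate or an expected ECI risk difference, so there is nothing to reproduce for this point. The only figure used below is the Part 2 size of 100 per arm. Its stated 80% power (difference 10, SD 25, 2-sided 0.05) reproduces: 10 / (25 × √(2/100)) = 2.83, and Φ(2.83 − 1.96) = 0.807; the noncentral t gives 0.804.

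**How the wider list changes the estimate.** For each arm, let T be the number of participants with at least one Grade ≥3 transaminase term. Let B be the number with a Grade ≥3 bilirubin or liver-function-test term and no transaminase term. Each participant counts once, so category incidence is (T + B)/n, and with equal arms

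RD(category) = RD(transaminase) + (B on volixibat − B on placebo)/n.

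Participants with both kinds of event add nothing to B. The point estimate moves only if B differs between arms, but any non-zero B changes the incidence and the CI.

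**Range under assumed counts.** Take n = 100 per arm and T = 8 (volixibat) v 2 (placebo). These counts are assumptions. The exact CIs invert two one-sided exact tests on the score statistic.

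| B, volixibat v placebo | Category count | RD, points | Exact 95% CI |
|---|---|---|---|
| 0 v 0 | 8 v 2 | +6.0 | −0.3 to 13.4 |
| 2 v 2 | 10 v 4 | +6.0 | −1.4 to 14.3 |
| 0 v 2 | 8 v 4 | +4.0 | −3.1 to 11.6 |
| 0 v 4 | 8 v 6 | +2.0 | −5.7 to 10.0 |

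The shift can also go the other way: B of 2 v 0 gives (10 − 2)/100 = +8.0 points.

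**Can the preferred-term tables replace the restricted row?** No. A participant with both an ALT and an AST event appears in both rows. If one arm's rows show a and b participants, the number with either event can lie anywhere from max(a, b) to a + b. With 8 and 8, that is 8 to 16. The per-term rows therefore do not give participant-level transaminase incidence, and SAP Section 7.1.7 does not commit to a risk difference for the restricted set.

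**The case against.** A reader might infer more than the mismatch: that worsening cholestasis will enter the category, load the placebo arm and mask a transaminase excess on volixibat. The documents do not support that.

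- Protocol Section 9.2.8.1 keeps ICP worsening out of AE data unless it is atypical, considered drug-related or of uncertain cause. Section 9.1.1 excludes disease-related laboratory findings unless they are more severe than expected. Exclusion criterion 15 removes women with total bilirubin above 1.3 mg/dL at screening, and the ECI needs Grade ≥3. The filter is not complete, but it blocks most of that route.
- Protocol Section 2.1 says that aminotransferases also rise in ICP, so the terms do not split cleanly into cholestatic and hepatocellular signals.
- No rates are given, so counts that cancel exactly would be invented.
- An ALT or AST excess would still show in the preferred-term tables and listings, the exposure-adjusted rates, and the laboratory summaries and shift tables (SAP Sections 7.1.6.1, 7.1.7, 7.2.1 and 7.2.2).

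Three further points have weight. A broad hepatic list is defensible in itself: Section 9.2.7 mentions possible drug-induced liver injury, Appendix 3 uses bilirubin as a trigger, and dropping the liver-function-test terms altogether could lose transaminase rises that were coded non-specifically. The SAP does not say whether the risk difference is per term, per category or overall; if it is per term, it is unaffected. And the statement in SAP Section 7.6 cannot be shown to be wrong, because the SAP is based on protocol Version 1, whose ECI wording is not available here.

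These arguments support keeping the bilirubin and liver-function terms in the analysis. They do not support reporting them under the transaminase label. Section 10.4.2.1 asks for terms for the ECIs as the protocol describes them, and adding a further ECI is different from widening a named one.

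**Conclusion.** The point holds as a definitional mismatch between the current protocol and the SAP. Only 6 of the 13 terms match the protocol's ECI, and a participant with no transaminase event can be counted under it. An incidence for this category, or a risk difference if computed by category, would estimate something broader than its name.

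The size and direction of the effect are unknown. In the illustration the risk difference ranges from +2.0 to +8.0 points around a restricted value of +6.0, with no change when the extra participants are absent or balanced between arms. That range depends wholly on assumed counts. Neither a masked hepatic signal nor a false statement of no deviations is established.

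The comparison is descriptive, with no test or margin. The point is minor, but worth correcting because the correction is nearly free.

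**What to change.** In SAP Appendix 2, restrict the transaminase category to the six ALT, AST and transaminase terms. Report the five bilirubin and two liver-function-test terms in a separate hepatic row with the same risk difference and exact 95% CI. If a combined hepatic group is wanted, show it as an additional row under a name that fits. In SAP Section 7.1.7, state that the risk difference is computed at participant level for each ECI category.

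The cost is a relabelled term list, one extra table row and one sentence. No data are lost and none need be collected. The SAP needs revision in any case: it still describes a three-arm, double-blind Part 1, whereas the current protocol has a two-arm, open-label one.
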